### 5.2.1 ASSESSMENTS OF COMMON PREGNANCY, BIRTH AND NEONATAL EVENTS

The following common pregnancy, delivery, and neonatal events should be recorded in source documents (clinic notes or CRFs) if they occur and *are only requested be recorded on AE worksheets if the PI or MD delegate feel that the event may be drug related* and/or determine that a full assessment is required.

#### Prenatal Maternal Events:

- Accidents or injuries
- Anaemia
- Back pain
- Bacterial or viral infections
- Contractions
- Diabetes and associated complications
- Gestational hypertension/ worsening of hypertension
- Heartburn
- Hemorrhoids; varicosis
- Hospitalization for obstetrical reasons
- Hypoglycemia requiring treatment
- Leg muscle cramps
- Ligament pail
- Pre-eclampsia and eclampsia
- Vaginal bleeding or discharge

- Birth injury
- Neonatal aspiration, hypoxia
- Respiratory distress of newborn
- Hyperbilirubinemia
- Neonatal hypoglycemia
- Neonatal Infection
- Hospitalization for observation after birth
- Hypoglycemia requiring treatment
- Genetic disorder

#### Intrapartum and Postpartum Maternal Events

- Hospitalization for delivery
- Anesthesia-related complications
- Cesarean delivery
- Hysterectomy
- Postpartum depression
- Postpartum hemorrhage
- Infections
- Ventilation
- Birth related complications

#### Infant Events:

**5.3 ADVERSE EVENT REPORTING.** Completed AE worksheets of all documented events will be captured on REDCap. All SAEs irrespective of their relatedness to the therapy or study procedures must be reported to the Sponsor. The site investigator must pursue any AE and if possible obtain information adequate both to determine the outcome and assess the relatedness to treatment so it can be determined by the PI and Sponsor whether it meets the criteria of a SUADR.

**Serious Unexpected Adverse Drug Reaction (SUADR):** All noxious and unintended responses to an investigational product related to any dose which is serious and unexpected.

## REPORTING PROCEDURES

Any SAE (irrespective of relatedness to study procedures) must be notified to the study Sponsor (SickKids) immediately upon the investigator becoming aware of the event (see guidelines below).

Completed SAE reporting forms are to be sent to:

- **Sponsor (SickKids) via [contact] or E-mailed to [[contact]](mailto:[contact])**

SERIOUS ADVERSE EVENTS (Recorded by site investigator)	REPORTING BY SITES TO SPONSOR	REPORTING BY SITES TO LOCAL REB
Unexpected , possibly, probably or definitely related to medication or study procedures	
 
• Notification within 24 hours
 
• Full report to follow as requested by the Sponsor
 
	
 
• According to Institutional guidelines
 

Expected , possibly, probably or definitely related to medication or study procedures	
 
• Notification within 24 hours
 
• Full report to follow as requested by the Sponsor
 
	
 
• According to Institutional guidelines
 

SAEs assessed to be unrelated to medication or study procedures	
 
• Notification within 24 hours
 
• Follow-up report only if requested by the Sponsor
 
	
 
• According to Institutional guidelines
 

The Sponsor will work with the National Coordinating centers in each regulatory jurisdiction to report events as required to the appropriate regulatory authority.

**5.4 EARLY STOPPING RULE.** All three RCT sub-studies, individually or as a group, can be temporarily stopped for safety reasons at any time, at the discretion of the Data & Safety Monitoring Board [*DSMB Charter*; also see 6.4]. An RCT can be stopped for benefit at the time of an interim analysis if results unequivocally favor one treatment arm over the other at the  $p < 0.001$  level. If one is demonstrably superior to the other, it would be unethical to continue the sub-study as is. Stopping of the study for benefit will be decided based on discussions of the DSMB with the study PI and the Trial Steering Committee.

## 6. STUDY MANAGEMENT & RESPONSIBILITIES

**6.1 MEDICAL OVERSIGHT** (Medical oversight) of participants at each study site will be the responsibility of the PI at each centre. Procedures for medical oversight must be implemented at each site and responsibilities in care and assessments delegated to appropriately trained staff. Documentation of this oversight must be maintained for the length of the trial (as required by your institution and regulatory authority).

**6.2 TRIAL OVERSIGHT** will be maintained by the Sponsor-Investigator, *[name]*.. He and his team of physicians and trial support staff will oversee the conduct of the study.

**6.3 DATA MANAGEMENT.** The password-protected REDCap data management system ([www.project-redcap.org](http://www.project-redcap.org)) will be used to enter de-identified patient data by the participating sites. Credentialing to access REDCap will be managed centrally by the FAST Trial study team in cooperation with the Cardiovascular Data Management Centre (CVDMC). Individual access will be limited to data from individual sites. The system is deployed through a secured/encrypted server hosted at SickKids and will be managed by an experienced Clinical Research Project Manager (statistician and database manager) from the CVDMC. REDCap is available anytime, anywhere in the world, is completely automated and will allow new patient input and randomization instantaneously once a center becomes eligible to participate in the FAST Therapy Trial; thereafter all required CRFs (incl. patient characteristics, treatment information, outcomes) will be available with basic data validation at the time of data entry (physiological range, validation of time interval, pre-determined coding, required fields, etc.). Regular updates of key findings will be requested from the site investigator up to 1 month of life. Once completed, participant data will be verified for completeness and validity by the FAST Trial team, and any queries will be sent to the site investigator. Once the record is deemed complete/valid, it will be locked so that further edits will not be possible to ensure highest data quality.

and providing logistic support to sites if required. The study sponsor will assist all sites including centers of countries without a national coordinator.

## 7. CONDUCT OF THE RCTs

The Table of Events below summarizes the different study steps from the time of prenatal identification and randomization to study end as they relate to the RCT sub-studies.

Procedures and Tests	Pre-treatment	Fetal Treatment		Postnatal Birth to 30(+) days
		Day 1	Day 2 - Birth	
Fetal echo: Diagnosis -SVA (M-mode; Doppler) - Fetal state	X diagnosis and data ⬆ Images within 1 week recommended		X data each visit ⬆ if changed	
Maternal 12-lead ECG	X required prior to treatment start ⬆		X recommended within 1 week of treatment start and repeated at every significant change in treatment/increase in dose ⬆ if changed	
Maternal exams: - BP, HR	X		X recommended within 1 week of treatment start and during maintenance therapy	
Maternal tests: - K, Ca - serum creatinine	X			
Maternal and pregnancy history	X			
Maternal consent	X			
Eligibility Assessment - PI	X			
Randomization	By sites in REDCap			
Hospitalization		Recommended	If indicated	If indicated
Treatment initiation		X		
Review of current treatment - Drugs, dosages, intervals			X each visit	X
Review of clinical findings			X each visit	X
Review of test results - Digoxin level (if relevant)			X each visit	
- Home fetal heart rate monitor (FHRM)			⬆ or enter data	
Adverse event assessment			X each visit	X
Compliance assessment (1st line therapy)			X each visit	
Review of prenatal outcome			X at birth/IUD	
Neonatal 12-lead ECG in sinus rhythm				X ⬆
Neonatal 12-lead ECG tracing in SVA				X ⬆ if present
Review of neonatal outcome				X at 30(+)days/NND
Review of maternal outcome				X

X = data entry into REDCap, ⬆= uploaded in REDCap

Patient identification, data entry, eligibility screening, randomization (Pre-treatment) and treatment initiation (Day 1) are to occur on the same day if there is an immediate need of fetal treatment.

**7.1 PATIENT IDENTIFICATION.** The site investigator will be responsible for identifying and recruiting RCT participants and conducting the study at the participating center. The investigator will inform a patient who fulfills eligibility criteria about the study early on with the help of a *Patient Brochure*.

Study Logs for screening and enrolment are to be kept securely at sites with access only to FAST study team members. These Logs will be de-identified prior to inspections and audits or if requested by the Sponsor for monitoring purposes. De-identification is also necessary before being sent to the Sponsor at end of study.

A *Screening Log* of all patients screened should be kept with the following information: screening date, patient name, institutional number, confirmation of sub-study screened for, eligibility status, enrolment status and a reason if not enrolled.

Once patients have consented to participate in the study, screened for eligibility and are enrolled into the study, their information should be entered into an *Enrolment Log* with the following information: participant's name, study ID number, institutional number, date and time of enrolment, study enrolled in, as well as an indication if and why a participant has withdrawn. Once a baby is born to a mother in the study, sites will need to keep a *Child Enrolment Log* with the child's name and institutional number, as well as the mother's corresponding study ID number.

**7.2 ELIGIBILITY CRITERIA.** Subjects are eligible for participation in an RCT sub-study if they meet ALL of the following inclusion criteria and NONE of the exclusion criteria. All subjects will be screened by Investigators for study eligibility prior to randomization and enrolment.

**INCLUSION CRITERIA:**

- Mother has provided written informed consent to participate in the RCT
- Fetal AF *without* hydrops (RCT A) or SVT *without* hydrops (RCT B) or SVT *with* hydrops (RCT C)
- Tachyarrhythmia that is significant enough to justify immediate transplacental pharmacological treatment:
  - Tachycardia  $\geq 170$  bpm during  $\pm 100\%$  of time ( $\leq 30$  0/7 weeks of gestation)
  - Tachycardia  $\geq 180$  bpm during at least 10% of observation time
  - Tachycardia  $\geq 280$  bpm
  - Tachycardia with fetal hydrops
- Gestational age  $> 12$  0/7 weeks and  $< 36$  0/7 weeks at time of enrolment
- Untreated tachycardia at time of enrolment
- Singleton Pregnancy
- Healthy mother with  $\pm$  normal pre-treatment cardiovascular findings:
  - ECG within normal range (sinus rhythm; QTc  $\leq 0.47$ s; PR  $\leq 0.2$  s; QRS:  $\leq 0.12$  s; insignificant anomalies; isolated premature beats; isolated complete right bundle branch block; non-specific ST-T segment changes allowed)

- Maternal resting heart rate of 50 bpm or above
- Maternal systolic BP of 85 mm Hg or above

#### EXCLUSION CRITERIA:

- AF *with* hydrops (condition is too infrequent to be studied in a separate RCT sub-study; eligible for Registry)
- Any maternal-fetal conditions associated with high odds of premature delivery or death other than tachycardia (e.g. severe IUGR; premature rupture of membrane; life-threatening maternal disease (incl. pre-eclampsia; HELLP syndrome); severe congenital fetal abnormalities (T 13 or 18; surgery or death expected < 1 month))
- History of significant maternal heart condition (open heart surgery; sick sinus syndrome; channelopathy (long QT, Brugada syndrome); ventricular tachycardia; WPW syndrome; high-degree heart block; cardiomyopathy)
- History of significant maternal obstructive airway disease including asthma
- Current therapy with the following medications:
  - antiarrhythmic drugs
  - Pentamidine
- Maternal serum potassium level <3.3 mmol/L / <3.3 mEq/L
- Maternal ionized serum calcium level of <1 mmol/L / <4 mg/dL) or total serum calcium level <2 mmol/L / <8mg/dL
- Maternal serum creatinine level > 97.2 µmol/L (>1.1 mg/dl)

**7.3 INFORMED CONSENT (IC)** The consent process at each site will be performed as approved by local REB or as per institutional practices. The study is explained to the patient in detail, including the alternatives (registry, non-participation) and any questions are answered prior to signing the consent form. The person obtaining consent must co-sign the form with date and time. A copy of the consent form must be given to the patient.

**7.4 PATIENT DATA ENTRY.** Completion of the enrolment and randomization process requires submission of the following baseline information into the patient's electronic REDCap form *prior* to any treatment:

- Name and center of the site investigator, incl. contact information
- SVA: date/gestational age at diagnosis, mechanism, pattern, rate and AV relationship
- Fetal state: presence/location of effusion(s), skin edema, and fetal movements
- Confirmation of enrolment into prospective randomized trial and selection of the sub-study
- Checklist of eligibility criteria for participation

Following randomization and treatment initiation, sites must upload *de-identified images* to REDCap that document the pretreatment fetal arrhythmia mechanism and health state (M-mode and/or Doppler still images, 2-dimensional images of the fetal abdomen/chest for proof of hydrops) and maternal 12-lead ECG for review by the Sponsor Echo Core Lab. Moving clips confirming the fetal SVA mechanism should also be sent via secure file transfer for review by the FAST Trial Echo Core Lab. If de-identification is not possible at the site, an arrangement can be made with the Sponsor to have images and clips sent via secure file transfer for de-identification prior to storage.

**7.5 DATA REVIEW.** Accurate differentiation between “AF vs. SVT” and “hydrops vs. non-hydrops” is critical for the randomization into the appropriate sub-study. SickKids will function as the Echo Core Lab Facility to review patient diagnosis and fetal state to determine if the initiated drug therapy is appropriate. The Core Lab provides support to ensure accurate diagnosis and classification and if requested will provide a review of findings within 48 hours. Other Core Lab physicians or steering committee members will arbitrate if there is no agreement in diagnosis with the site investigator. This approach will avoid inaccuracies in diagnosis and study results.

**7.6 RANDOMIZATION TO FIRST LINE THERAPY.** An individual ID code is assigned by REDCap at first data entry to protect patient privacy. Once participant screening, eligibility data, and confirmation of consent data has been entered into REDCap, they will be asked to confirm diagnosis and then be allowed to randomize to a drug assignment in the selected treatment arm.

Participants will be randomized into one of two possible 1st line therapy arms, which either will be started as monotherapy (AF or SVT without hydrops) or as dual therapy (SVT with hydrops). First line drug therapy is pre-defined including the initial dose and mode of administration:

### **AF WITHOUT HYDROPS (RCT A): DIGOXIN vs. SOTALOL**

#### **RCT A ARM 1: DIGOXIN**

Aim: therapeutic maternal trough level of 1.0-2.0 ng/ml or 1.3-2.6 nmol/L (please verify the units your laboratory reports).

→ *Oral or intravenous* loading dose: **Initiate treatment with 0.5 mg Digoxin q 12 h** (total 4 doses over 48 hours) followed by:

→ *Oral maintenance dose:* it is recommended to obtain maternal digoxin trough level 12 hours after the 4th loading dose just prior to the administration of the 1st maintenance dose\* → await the result and adjust the 1st maintenance dose according to the trough digoxin level as followed:

(\*alternatively, a digoxin level may be obtained prior to the 4th dose to adjust the 1st maintenance dose if levels are not rapidly measured in your center)

Trough level (nmol/L)	Trough level (ng/ml)	Maintenance digoxin dose	Route
2.6 to <2.9	2 to <2.3	0.25 mg/day	Oral
1.9 to <2.6	1.5 to <2	0.375 mg/day	Oral
1.5 to <1.9	1.2 to <1.5	0.5 mg/day	Oral
1.0 to <1.5	0.8 to <1.2	0.75 mg/day	Oral
<1.0	<0.8	1 mg/day	Oral
≥2.9	≥2.3	0 mg/day until digoxin level is <2 ng/ml	

→ recommended to repeat maternal trough level until steady state therapeutic drug levels are obtained. *If using IV Digoxin loading see additional recommendations for IV Digoxin administration below.*

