## 5. STUDY SAFETY

**5.1 SAFETY PROCEDURES.** The FAST RCTs will assess *standard prenatal treatment* that has been used for decades because the fetus suffers from a life-threatening yet treatable cardiac condition and other management options including direct treatment or premature delivery are considered more invasive, more harmful, or both. Perinatal demise is not an unusual outcome of hydropic fetuses with SVA, irrespective of the choice of treatment. Health Canada, FDA (US) and MHRA (UK) have approved all three RCT sub-studies. There is extensive data on the safe use of the study agents for this indication. Minor drug-related maternal AEs are not infrequent [monographs], but maternal SAEs owing to fetal antiarrhythmic drug therapy have not been reported. However, virtually all antiarrhythmics have proarrhythmic potentials to provoke new or exacerbate existing

arrhythmias. This risk increases with toxic drug levels, maternal heart disease, preexisting ventricular arrhythmia, and hypokalemia.

Procedures for study participants to minimize the risk of SAEs include:

- only mothers without serious health and pregnancy concerns other than fetal SVA are eligible for participation in RCT sub-studies (**see 7**);
- the primary physician and participant both are informed about the assigned drug therapy from the time of randomization to study end (open label trial);
- drug dosages will be used that are considered to be safe and effective, thus avoiding toxic levels (digoxin) and excessive QTc prolongation >0.5 (sotalol); d) concomitant medication (7.6.2) that may interact with a study drug are not to be used or, if no alternative exists, used with caution during the trial; and
- initiation of therapy is recommended in-hospital to monitor maternal/fetal heart rates and wellbeing, followed by serial outpatient encounter once arrhythmia control is achieved.

**5.2 ADVERSE EVENT ASSESSMENT AND DOCUMENTATION.** A main objective of FAST RCTs is patient safety. This is accomplished by the systematic recording of AEs.

**Adverse Event (AE):** is defined as **any untoward medical occurrence of a symptom that may or may not have a causal relationship with the treatment used.** Examples include a rash noted during a physical exam, abnormal lab results, or a change from a baseline condition.

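### In RCT A and B one digoxin level-to-dose table is read with a level drawn either after or before the 4th loading dose, so draw time alone can move a mother to a higher-dose row or out of the zero-dose row

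*Combined protocol and SAP*

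**What the plan says.** Section 7.6, RCT A Arm 1 (digoxin), describes loading as "Initiate treatment with 0.5 mg Digoxin q 12 h", with "total 4 doses over 48 hours) followed by" oral maintenance. For the first maintenance dose, "it is recommended to obtain maternal digoxin trough level 12 hours after the 4"th loading dose, just before maintenance starts. The site waits for the result and reads the dose from a table of trough bands.

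A footnote attached to that instruction adds: "alternatively, a digoxin level may be obtained prior to the 4"th dose, to adjust the 1st "maintenance dose if levels are not rapidly measured in your center".

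One table follows. Its top band, at or above 2.3 ng/ml, gives "0 mg/day until digoxin level is <2 ng/ml". The next bands down are 2 to <2.3 ng/ml (0.25 mg/day) and 1.5 to <2 ng/ml (0.375 mg/day). The lower bands give 0.5, 0.75 and 1 mg/day. After the table, it is "recommended to repeat maternal trough level until steady state therapeutic drug levels are obtained".

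RCT B Arm 1 has the same instruction, footnote and table. RCT C, with 8-hourly loading, describes only a trough after the 4th dose.

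Sections 2.6 and 5.1 list the choice of drug dosages among the measures that limit serious adverse events, "thus avoiding toxic levels (digoxin").

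**The concern.** The two permitted samples measure different things. The recommended trough follows four doses (2.0 mg in total). The alternative follows three (1.5 mg), and the footnote uses it only for the maintenance dose, so the 4th loading dose still follows. The sentence leading into the table describes the later sample, and nothing says how its bands apply to the earlier one.

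If the earlier level is systematically lower, the displacement goes one way: toward a higher maintenance dose, or out of the band that gives no digoxin. That band is the table's explicit upper-level protection. First maintenance dosing in the digoxin arms of RCT A and B would then depend partly on how fast a site's laboratory works. Section 7.8 lists the digoxin level among the captured items but names no draw time relative to the loading doses, so the two kinds of reading might not be separable afterwards.

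**Working it through.** **Inputs from Section 7.6 (RCT A; identical in RCT B).** Dose 0.5 mg, interval 12 h, four doses; bands cut at 0.8, 1.2, 1.5, 2.0 and 2.3 ng/ml.

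**Assumptions not in the documents.** Linear one-compartment kinetics with equal doses; the early draw taken just before dose 4, that is 12 h after dose 3 (the footnote says only that it precedes dose 4); and maternal half-life T, for which no figure is given, so a range is shown.

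**The plan's own schedule.** Doses fall at 0, 12, 24 and 36 h. The trough 12 h after dose 4 is at 36 + 12 = 48 h, which reproduces the stated 48 hours. Cumulative dose is 4 × 0.5 = 2.0 mg. The early draw is at about 36 h, after 3 × 0.5 = 1.5 mg.

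**Ratio of the two troughs.** With r = 2^(−12/T), the trough after n equal doses is proportional to r + r² + … + rⁿ. Hence

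post-4th / pre-4th = R = (1 − r⁴)/(1 − r³).

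Example at T = 36 h: r = 0.794, r³ = 0.500, r⁴ = 0.397, so R = 0.603/0.500 = 1.206 and the inverse is 0.83.

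| Assumed T | R | pre/post (1/R) | Pre-4th reading if post-4th is 2.3 ng/ml | Row then used | Post-4th troughs that miss the zero-dose row (2.3 to 2.3 × R) |
|---|---|---|---|---|---|
| 12 h | 1.07 | 0.93 | 2.15 | 0.25 mg/day | 2.3 to 2.46 |
| 24 h | 1.16 | 0.86 | 1.98 | 0.375 mg/day | 2.3 to 2.67 |
| 36 h | 1.21 | 0.83 | 1.91 | 0.375 mg/day | 2.3 to 2.77 |
| 48 h | 1.23 | 0.81 | 1.86 | 0.375 mg/day | 2.3 to 2.84 |
| 72 h | 1.26 | 0.79 | 1.82 | 0.375 mg/day | 2.3 to 2.91 |
| no elimination | 1.33 | 0.75 | 1.72 | 0.375 mg/day | 2.3 to 3.07 |

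R exceeds 1 for every half-life above zero, so under these assumptions the direction is fixed and only the size depends on T. At a very short half-life the difference nearly vanishes (R = 1.01 at 6 h).

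**Around the aim of 1.0–2.0 ng/ml.** At T = 36 h, a pre-4th reading of 1.95 ng/ml lies inside the aim and in the 0.375 mg/day row. It corresponds to 1.95 × 1.206 = 2.35 ng/ml after dose 4, in the zero-dose row.

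**How many levels change row.** On an even grid of post-4th troughs from 0.8 to 3.0 ng/ml, 25% change row at T = 12 h, 56% at 24 h, 68% at 36 h, 75% at 48 h and 82% at 72 h. The grid is illustrative and is not a patient distribution. A one-row move between non-zero rows raises the daily dose by 50% (0.25 to 0.375, or 0.5 to 0.75) or 33% (0.375 to 0.5, or 0.75 to 1). Those percentages apply only to mothers who change row.

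**The case against.** A reader might infer that the two sampling times contradict each other. The text does not support that. The footnote is an explicit alternative with a stated purpose and a stated condition, and it can be read as a deliberate choice to use the same bands for both draws. What remains is that the protocol neither says so nor explains how one set of bands suits two samples one loading dose apart.

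A reader might also infer that mothers at slow-laboratory sites are all placed in a higher-dose row. They are not: a mother well inside a band stays in it, and at a 12 h half-life three quarters of the illustrative grid does not move. The size rests on a half-life the documents do not give, and they also give no frequency for levels at or above 2.3 ng/ml.

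There are general safeguards. Repeat troughs are recommended until steady state, Section 7.7 recommends starting treatment in hospital with digoxin levels among the monitoring and lets the physician adjust the dosage at any time, and the Table of Events lists review of digoxin levels at each visit. These limit how long a misplacement lasts. None is tied to the early draw, and they can correct a misplacement only after the first maintenance dose has been set. Repeat results may also be slow at the very centers the footnote addresses.

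Finally, nothing here shows an effect on the primary outcome, the analysis or the sample size. That objection stands in full.

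**Conclusion.** The point holds as a question of dosing consistency and maternal safety in the digoxin arms of RCT A and B. One table serves two non-equivalent samples, and following the footnote as written can move a mother in one direction because of draw time alone. The early reading is about 7% lower at an assumed half-life of 12 h, 14% at 24 h, 17% at 36 h and 19% at 48 h, and at most 25% lower. At 36 h, post-4th troughs from 2.3 to about 2.8 ng/ml would miss the zero-dose row until a repeat level is available.

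This rests on linear kinetics, equal doses, an early draw taken just before dose 4, and the assumed half-life. The frequency is unknown. It would be too strong to conclude that the dosing scheme produces toxic levels: the documents neither report such levels nor allow their rate to be estimated. The change is a cheap improvement; it does not correct a flaw in the trial's inference.

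**What to change.** In Section 7.6, for RCT A and RCT B, state which sampling time the table's bands refer to. Have the clinical and pharmacology leads reconcile the option of drawing before the 4th dose with that table, and write the result into both arms. In REDCap, record with each digoxin level the draw time relative to the loading doses, so that early and late readings can be told apart. Which bands, doses or sampling rule should apply is for those leads to decide; none is proposed here.

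The cost is a clarification of one section, repeated in two arms, and one data field. The randomization, endpoints, analysis and sample size stay as they are.
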